5.2 Initial dose and schedule

5.2.1 Study Drug Administration

Patients are registered to the study when they sign the PISIC. For groups A and B, patients must have a central assessment of MGMT testing after registration. Once MGMT status is confirmed, the site is informed by a notification e-mail, and proceeds to the next step to enroll the patient into either group A or group B. Please see section 13.1.2 for detailed information.

Dosing calendars can be found in Appendix H.

5.2.1.1 Group A

Patients with MGMT promoter-unmethylated AA or GBM will receive TG02 orally twice weekly in combination with radiation therapy (RT).

TG02 and RT can start on the day of enrollment but no more than 7 days after enrollment. TG02 will be administered on days 1, 4, 8, 11, 15 and 18. Standard involved-field hypofractionated RT will be administered at 39.9 Gy in 15 fractions of 2.66 Gy for 3 weeks (days 1-21).

Seven days after completing combination therapy, patients will receive maintenance cycles of single agent TG02. TG02 will be administered on days 1, 4, 8, 11, 15, 18, 22 and 25 of each 28-day maintenance cycle.

DOSE ESCALATION

The dose escalation scheme for TG02 is provided below. Three patients will be enrolled at 100 mg.

- If no patient in this cohort of 3 patients experiences a DLT, the dose will be escalated and 3 patients enrolled at 150 mg.
- If 1 patient in the cohort of 3 patients experiences a DLT, 3 additional patients will be enrolled at 100 mg. If none of the additional 3 patients experiences a DLT, the dose will be escalated and 3 patients enrolled at 150 mg.
- If the DLT criteria are not met (i.e., no patients with DLT out of 3 patients or ≤ 1 DLT out of 6 patients) at 150 mg, then, 150 mg TG02 will be declared the MTD for expansion.
- If > 1 out of 3 patients or ≥ 2 out of 6 patients experiences a DLT at 150 mg, dose escalation will not proceed and 100 mg will be considered the maximum MTD.
- If > 1 out of 3 patients or ≥ 2 out of 6 patients experiences a DLT at 100 mg, the arm will be closed

Patients who have not experienced any DLTs at the end of their first cycle will continue at the same TG02 dose for the subsequent cycles, unless they experience a severe side effect needing a dose reduction or delay (see section 5.5 for specific instructions).

TG02 Citrate Capsules Dose Escalation Scheme

Dose Level (Cohort)	Dose (mg)	# Units/ Capsule Strength (mg)	
		50	150
0	100	2	0
1	150	0	1

The Dose-Limiting Toxicity (DLT) for group A will be defined as any of the following adverse events occurring during cycle 1 that are considered clinically significant and there is a reasonable possibility that the AE is related to the combination treatment by the clinical investigator:

- Any non-hematological grade III–IV toxicity according to CTCAE, Version 5.0 with the exclusion of alopecia and asymptomatic or reversible laboratory abnormalities which can be rapidly controlled with appropriate measures. This acute toxicity must be declared as possibly related by the clinical investigator in order to be taken into account in the decision rule.
- An absolute neutrophil count $< 0.5 \times 10^9/L$ lasting for ≥ 7 days
- Febrile neutropenia defined as an absolute neutrophil count $< 0.5 \times 10^9/L$ and fever of at least $38.5^\circ C$
- Thrombocytopenia grade III with bleeding or any grade IV according to CTCAE, Version 5.0

- Nausea, vomiting or diarrhea grade III-IV not controlled after 48 h of maximal antiemetic or antidiarrheal treatment
- Any toxicity not qualifying for DLT but which does not allow intake of 75% of intended dose intensity of TG02 or of RT

EXPANSION

After dose escalation is completed, additional patients will be enrolled at MTD up to a total of 24 evaluable patients in Group A. Expansion at the predetermined MTD will be stopped if 2 or more of the first 6 patients, or 33% or more of the patients thereafter, experience a DLT. The expansion cohort will be fully enrolled at the next lower dose level. If there are again 2 DLT in the first 6 patients, expansion will be stopped in that arm.

5.2.1.2 Group B

Patients with MGMT promoter-methylated AA or GBM will receive TG02 orally twice weekly in combination TMZ.

TG02 can start on the day of enrollment but no more than 7 days after enrollment. TG02 will be taken on days -7, -4, 1, 4, 22 and 25 of a 28-day schedule. TMZ will be given in the standard 28-day cycle regimen (200 mg/m²) for 5 days q 28d.

DOSE ESCALATION

The dose escalation scheme for TG02 is provided below.

Three patients will be enrolled at 100 mg.

- If no patient in this cohort of 3 patients experiences a DLT, the dose will be escalated and 3 patients enrolled at 150 mg.
- If 1 patient in the cohort of 3 patients experiences a DLT, 3 additional patients will be enrolled at 100 mg. If none of the additional 3 patients experiences a DLT, the dose will be escalated and 3 patients enrolled at 150 mg.
- If the DLT criteria are not met (i.e., no patients with DLT out of 3 patients or ≤1 DLT out of 6 patients) at 150 mg, then, the data for the 100mg and 150 mg will be reviewed by an IDMC.
- If > 1 out of 3 patients or ≥ 2 out of 6 patients experiences a DLT at 150 mg, dose escalation will not proceed and 100 mg will be considered the maximum MTD.
- If > 1 out of 3 patients or ≥ 2 out of 6 patients experiences a DLT at 100 mg, the arm will be closed

Patients who have not experienced any DLTs at the end of their first cycle will continue at the same TG02 dose for the subsequent cycles, unless they experience a severe side effect needing a dose reduction or delay (see section 5.5 for specific instructions).

- TG02 Citrate Capsules Dose Escalation Scheme

Dose Level (Cohort)	Dose (mg)	# Units/ Capsule Strength (mg)	
		50	150
0	100	2	0
1	150	0	1

The Dose-Limiting Toxicity (DLT) for group B will be defined as any of the following adverse events occurring during cycle 1 that are considered clinically significant and there is a reasonable possibility that the AE is related to the combination treatment by the clinical investigator:

- Any non-hematological grade III-IV toxicity according to CTCAE, Version 5.0 with the exclusion of alopecia and asymptomatic or reversible laboratory abnormalities which can be rapidly controlled with appropriate measures. This acute toxicity must be declared as possibly related by the clinical investigator in order to be taken into account in the decision rule.
- An absolute neutrophil count $< 0.5 \times 10^9 / \text{L}$ lasting for ≥ 7 days
- Febrile neutropenia defined as an absolute neutrophil count $< 0.5 \times 10^9 / \text{L}$ and fever of at least 38.5°C
- Thrombocytopenia grade III with bleeding or any grade IV according to CTCAE, Version 5.0
- Nausea, vomiting or diarrhea grade III-IV not controlled after 48 h of maximal antiemetic or antidiarrheal treatment
- Any toxicity not qualifying for DLT but which does not allow intake of 75% of intended dose intensity of TG02 or of TMZ

EXPANSION

After dose escalation is completed, additional patients will be enrolled at MTD up to a total of 12 evaluable patients in Group B. Expansion at the predetermined MTD will be stopped if 2 or more of the first 6 patients, or 33% or more of the patients thereafter, experience a DLT. The expansion cohort will be fully enrolled at the next lower dose level. If there are again 2 DLT in the first 6 patients, expansion will be stopped in that arm.

EXPECTED TOXICITIES OF THE COMBINATION

Expected overlapping toxicities for TG02 and TMZ are gastrointestinal, hematological and hepatotoxicity. TG02 is being evaluated in combination with TMZ in a dose escalation study being conducted by the National Cancer Institute. In this study, TG02 has been dosed at either 200 or 250 mg on Day -3 prior to Cycle 1 and on Days 1, 12, 15, and 26 of each cycle. TMZ is dosed at 125 mg/m^2 7 days on and 7 days off (dosing days 1-7 and 15-21). Twelve (12) patients have been treated to date. The adverse events occurring in $>15\%$ of patients are provided in the following table (Ref. 57).

Description of AE	Adverse Events N (%)	
	All grades	Grades 3 and 4
ALT elevation	10 (83)	4 (33)
Leukopenia	10 (83)	4 (33)
Diarrhea	9 (75)	1 (8)
Lymphopenia	9 (75)	6 (50)
Fatigue	8 (67)	
Nausea	7 (58)	
AST elevation	6 (50)	
Neutropenia	6 (50)	5 (41)
Thrombocytopenia	6 (50)	
Vomiting	4 (33)	1 (8)

Description of AE	Adverse Events N (%)	
	All grades	Grades 3 and 4
Constipation	3 (25)	
Anemia	3 (25)	
Headache	2 (17)	

5.2.1.3 Group C

Patients will receive TG02 orally twice weekly at 150 mg on days 1, 4, 8, 11, 15, 18, 22 and 25. TG02 can start up to 7 days after registration/enrollment of the patient. The decision process for dose reductions is outlined in detail in section 5.5.3. The starting dose of TG02 will be reduced to 100 mg if 2 of the first 6 patients or 33% or more of the patients thereafter come off study treatment for any reason other than progression during the first three months. There will be no dose reduction below 100 mg and enrolment in arm C will be stopped.

5.2.1.4 Instructions for Study Drug Administration

TG02:

For all groups, TG02 will be taken as follows:

- TG02 citrate capsules should be swallowed whole with approximately 250 mL (one glass) of water while fasting, i.e., at least 1 hour before or 2 hours after a meal.
- TG02 should be taken approximately at the same time on each dosing day. For groups A and B, capsules should be taken approximately 1 hour before administration of TMZ or RT.
- A patient diary card for TG02 and TMZ should be given to and completed by patients
- Missed doses of TG02 and TMZ will be noted in the patient diary card and will not be replaced.
- Patients who vomit may be redosed with TG02 only if the TG02 capsules are still intact and visible in the vomitus and after appropriate antiemetic therapy has begun.
- Treatment compliance will be verified at each monthly visit using the study drug diary completed by patients and by a capsule count.

PROPHYLAXIS:

Nausea, vomiting and diarrhea are very commonly associated with TG02. Prophylaxis for nausea, vomiting and diarrhea are required. Please see section 5.6.2 for prophylaxis instructions.

PHOTOTOXICITY:

At present it is not yet established whether TG02 alone or in combination with other drugs might cause phototoxicity.

Nevertheless, patients should be advised to minimize UV light exposure for the duration of the TG02 use and to use sun protecting creams.

RT: For group A, see Section 5.7 for RT administration.

TMZ: For group B, TMZ will be administered at 200 mg/m² once daily for 5 days followed by 23 days without treatment.

Method of administration: as per local practice.

- Temozolomide hard capsules should be administered in the fasting state.
- The capsules must be swallowed whole with a glass of water and must not be opened or chewed.

- Nausea and vomiting are very commonly associated with TMZ. Anti-emetic therapy should be administered as per local practice.
- If vomiting occurs after the dose is administered, a second dose should not be administered that day.

Detailed guidelines for the management of toxicity are provided in the protocol in section 5.5 for TG02 and RT and section 5.7.8 for RT.

5.3 Treatment duration

Group A: combination treatment (TG02 and RT) will continue for 3 weeks. Maintenance cycles (TG02 single agent) will continue until disease progression or until the patient completes 12 cycles therapy.

Group B: combination treatment (TG02 and TMZ) will continue until disease progression or until the patient completes 12 cycles of therapy.

Group C: TG02 treatment will continue until disease progression or until the patients completes 12 cycles of therapy.

Treatment with TG02 may be continued beyond 12 cycles if there is no relevant toxicity, no progressive disease, and if the treating physician considers this to be of clinical benefit. The disease status will be regularly assessed according to the protocol during this period to evaluate the duration of response.

5.4 Withdrawal criteria

Patients discontinuing study therapy including RT in Group A and TMZ in Group B in the absence of progression should not receive any other cancer treatment before their disease progresses, unless this is clearly not in the interest of the patient.

After progression, treatment will be left to the discretion of the treating physician. Any further anti-cancer therapy will not be considered as part of the protocol treatment.

The principal investigator should discontinue study treatment for a patient in the event of:

- Progressive disease
- Intercurrent illness
- Unacceptable toxicity
- Protocol violation, loss to follow-up, patient significant non-compliance
- Pregnancy
- Study treatment interruptions, **i.e., more than 28 days delay of TG02**
- Administrative or other reasons

An end of study visit should be performed, and follow-up for survival collected, whenever feasible.

Patients have the right to withdraw from the study at any time for any reason

An excessive rate of withdrawals can render the study uninterpretable; therefore, unnecessary withdrawal of patients should be avoided. Please note that upon patient withdrawal from the study for any reason other than withdrawal of consent, end of study visit should still be performed, and follow-up for survival collected, whenever feasible.

Data collection and follow-up of patients after withdrawal of consent for study treatment

In the case that the patient decides to prematurely discontinue study treatment, the patient must be followed for disease assessments and survival follow-up, unless the patient decides to withdraw consent for the collection of these data. In the case that the patient withdraws consent, the patient must be asked if can still be contacted for survival follow-up only. The outcome of these discussions should be documented in both the medical records and in the eCRF.

5.5 Dose modifications following adverse events

5.5.1 RT Delays

RT-related toxicities should be managed as per local practice. RT dose modifications are not allowed per se, but information on managing delays is given in the radiotherapy section (section 5.7.8). In case of any AEs leading to RT interruption or delays not considered related to TG02, TG02 should continue as scheduled if medical condition allows it.

During dose escalation, an interruption of RT for >25% of the planned total dose in Cycle 1 will be considered a DLT (see section 5.2.1).

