5.5.2 TMZ

TMZ-related toxicities should be managed as per local practice. Dose modifications for TMZ are allowed and should follow the standard of care at the institution except as instructed in sections 5.5.3.2, 5.5.3.3 and 5.5.3.4 below. In case of any AEs leading to TMZ interruption or delays not considered related to TG02, TG02 should continue as scheduled if medical condition allows it. If TMZ is interrupted due to toxicity, upon its resolution, TMZ should be restarted only at the next cycle.

During dose escalation, an interruption of TMZ for >25% of the planned total dose in Cycle 1 will be considered a DLT (see section 5.2.1).

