5.5.3.2 Group A

5.5.3.2.1 Dose escalation phase

Cycle 1: no TG02 dose reductions are allowed in Cycle 1, except if a patient experiences a DLT.

Skipped doses for TG02 are allowed. A “skipped dose” for TG02 when RT is not interrupted means that one or more single doses will be omitted and not replaced, in order not to change the temporal relationship with RT.

For example, if TG02 is planned on days 1, 4, 8 but day 4 has to be omitted, TG02 can be restarted on day 8 if the AE is sufficiently resolved: TG02 is always restarted on a scheduled dose day. Skipping TG02 for >25% of the planned total dose in Cycle 1 will be considered a DLT (see section 5.2.1).

Toxicities possibly related to TG02 should be managed as outlined in the tables below.

Cycles 2+: TG02 dose reductions and skipped dose(s) can be made for adverse events as described in the tables below.

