5.5.3.3 Group B

5.5.3.3.1 Dose escalation phase

Cycle 1: no TG02 or TMZ dose reductions are allowed in Cycle 1 except if a patient experiences a DLT.

Skipped doses of TG02 are allowed. A "skipped dose" for TG02 when TMZ is not interrupted means that one or more single doses will be omitted and not replaced, in order not to change the temporal relationship with TMZ.

For example, if TG02 is planned on days 1, 4 and 22, but day 4 has to be omitted, TG02 can be restarted on day 22 if the AE is sufficiently resolved: TG02 is always restarted on a scheduled dose day.

Interruptions of TMZ are allowed.

Skipping TG02 or interrupting TMZ for >25% of the planned total dose in Cycle 1 will be considered a DLT (see section 5.5.1).

Toxicities possibly related to TG02 should be managed as outlined in the tables below. Toxicities of TMZ should be managed as outlined in the table below and per local practice, where noted.

Cycles 2+: TG02 dose reductions and skipped dose(s) can be made for adverse events as described in the tables below. TMZ dose reductions and interruptions can be made for adverse events as described in section 5.5.2 and the tables below.

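### The synopsis and section 8.1.1 give conflicting 75% rules for which cycle-1 patients count in the Group A/B 3+3 decision, and 8.1.1 has no exception for a patient whose low intake is itself the DLT

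*Combined protocol and SAP*

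**What the plan says.** Determining the MTD is a primary endpoint in Groups A and B (2.2.1). Several places bear on which cycle-1 patients feed that decision.

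- **Protocol summary, number of patients.** Toxicity can be assessed if dose intensity reaches 75% for one of the pair: TG02 or RT in Group A, TG02 or TMZ in Group B.
- **8.1.1, below the decision table.** Toxicity can be assessed if compliance reaches 75% for TG02 and for the partner treatment of the group.
- **7.1.1.** Compliance is defined for TG02 and TMZ, not RT. A patient with planned interruptions is not thereby noncompliant.
- **5.2.1.1 and 5.2.1.2.** A DLT must be "considered clinically significant and there is a reasonable possibility that the AE is related to the combination treatment". The last criterion is, for Group A, "Any toxicity not qualifying for DLT but which does not allow intake of 75% of intended dose intensity of TG02 or of RT" and, for Group B, "Any toxicity not qualifying for DLT but which does not allow intake of 75% of intended dose intensity of TG02 or of TMZ".
- **5.5.1, 5.5.2, 5.5.3.2.1 and 5.5.3.3.1.** Four sentences treat a cycle-1 shortfall above 25% as a DLT during escalation, without naming a cause. For RT: "During dose escalation, an interruption of RT for >25% of the planned total dose in Cycle 1 will be considered a DLT (see section 5.2.1". For TG02 in Group A: "Skipping TG02 for >25% of the planned total dose in Cycle 1 will be considered a DLT". The Group B sentence points elsewhere: "Skipping TG02 or interrupting TMZ for >25% of the planned total dose in Cycle 1 will be considered a DLT (see section 5.5.1".
- **8.1.1, replacement.** Patients are replaced if, before cycle 1 ends, they progress, die of their disease, or leave the study for a reason other than a DLT.
- **8.2.1.** Replaced patients are not in the safety population.

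**The concern.** The two 75% rules cannot both be applied. One is satisfied by either treatment and the other needs both. One is framed as dose intensity and the other as compliance, which under 7.1.1 can be intact even when the dose received is low.

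The possible errors favour clearing a dose. Under the synopsis, a patient who had full RT and little TG02 for a non-toxic reason counts as a patient without DLT, although he or she says little about the combination. Under 8.1.1 read literally, a patient whose toxicity prevented 75% intake fails the condition for assessment, although 5.2.1 makes that event a DLT.

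In a 3+3 with two dose levels, one patient's classification can decide a level. A non-DLT patient below 75% who stays on study is also not on the replacement list, so the plan does not say how the cohort is completed.

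**Working it through.** The plan states no operating characteristic for the 3+3, so there is no figure to reproduce.

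**1. Where 75% falls.** Planned cycle-1 treatment is 6 TG02 doses in each group (5.2.1.1, 5.2.1.2), 5 TMZ days, and 15 RT fractions (5.7).

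- TG02: 1 of 6 missed = 16.7%; 2 of 6 = 33.3%, leaving 66.7%.
- TMZ: 1 of 5 = 20%; 2 of 5 = 40%.
- RT: 3 of 15 = 20%; 4 of 15 = 26.7%, leaving 11/15 = 73.3%.

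Two TG02 doses, two TMZ days or four fractions therefore cross the limit.

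**2. The rules side by side (Group A).**

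| Cycle-1 patient | Synopsis | 8.1.1, 75% figure | DLT under 5.2.1? |
|---|---|---|---|
| 4/6 TG02, 15/15 RT, unrelated cause | assessable | not assessable | no |
| 1/6 TG02, 15/15 RT, unrelated cause | assessable | not assessable | no |
| 6/6 TG02, 11/15 RT, unrelated cause | assessable | not assessable | no |
| 4/6 TG02, 15/15 RT, related toxicity prevented intake | assessable | not assessable | yes |
| 4/6 TG02, 11/15 RT, related toxicity prevented intake | not assessable | not assessable | yes |

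If compliance in 8.1.1 is read as in 7.1.1, rows 1, 2 and 4 may become assessable. The last row shows that the synopsis has no DLT exception either, but there both treatments must be below 75% before it matters.

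**3. Size in limiting cases.** The documents give no DLT rate for 100 or 150 mg, so p below is assumed.

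(a) *Under-exposed patient counted as clean.* If that patient could not have had a DLT, a DLT-free cohort of 3 rests on 2 patients: (1−p)² instead of (1−p)³. This is the extreme. A patient with 4 of 6 doses still carries some risk, so the effect is smaller.

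(b) *Dose-intensity DLT dropped under literal 8.1.1, the other two patients clean.* If counted, the cohort is 1 of 3 and passes only with no DLT in three more: (1−p)³. If dropped and one patient is added, the cohort passes with probability (1−p) + p(1−p)³.

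| Assumed p | (1−p)³ | (a) (1−p)² | (b) (1−p) + p(1−p)³ |
|---|---|---|---|
| 0.20 | 0.512 | 0.640 | 0.800 + 0.102 = 0.902 |
| 0.33 | 0.301 | 0.449 | 0.670 + 0.099 = 0.769 |
| 0.40 | 0.216 | 0.360 | 0.600 + 0.086 = 0.686 |

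Both columns are conditional on such a patient arising. They do not say how often that happens.

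**4. Replacement load.** Let q be the assumed share of non-DLT patients below 75%, taken as 2% and 5%.

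- At least one in a cohort of 3: 1 − (1−q)³ = 0.059 and 0.143.
- Expected in 12 escalation patients (two levels of 6): 12q = 0.24 and 0.60.
- Two or more in 12: 0.023 and 0.118.

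**The case against.** **The rules can be reconciled by sense.** The synopsis wording may be a loose rendering of 8.1.1. Section 5.2.1 expressly makes toxicity-driven low intake a DLT, and the decision table counts DLTs, so a sensible team would not drop such a patient. A minimum of 3 patients per level and totals given as evaluable patients suggest that an uninformative patient is made up. The study team reviews each cohort (18.1), and in Group B the IDMC reviews both dose levels if 150 mg passes (5.2.1.2). Most of this stands and limits the harm. However, evaluable is not defined, and the reviewers have no single criterion. They would choose between two written rules with the data in view.

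**A stronger reading is tempting.** A reader might infer that the four sentences in 5.5 make any shortfall above 25% a DLT, whatever its cause, and so bias escalation towards failure. With assumed DLT rates of 10% and 15% at 100 and 150 mg, counting a 2–5% non-toxic shortfall as DLTs would lower the probability that both levels pass from 74% to 68–60%. The documents do not support presenting this as the expected effect:

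- The heading of 5.5 concerns modifications after adverse events.
- The Group A skip example is about an event resolving: "TG02 can be restarted on day 8 if the AE is sufficiently resolved".
- More than 25% not taken is the complement of the 75% intake in 5.2.1.
- Three of the sentences cite 5.2.1, and the Group B sentence reaches it through 5.5.1. Section 5.5.2 gives the TMZ limit with the correct pointer.
- Every rate in that calculation is assumed.

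The stronger reading also conflicts with the replacement gap. If 5.5 were literal, every such shortfall in escalation would already be a DLT, leaving essentially no non-DLT patients below 75% to replace.

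**Conclusion.** The concern holds as an inconsistency between the Protocol summary and 8.1.1 on who is assessable for a primary-endpoint decision, together with a missing DLT exception in 8.1.1. This takes 5.2.1 as governing what a DLT is.

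The conflict is on the face of the text and needs no assumed rates. Its effect on the MTD cannot be estimated, because the documents give neither a shortfall rate nor DLT rates at 100 and 150 mg. The limiting cases show only that one misclassified patient can matter. The replacement gap is secondary, being partly covered by the 3-patient minimum. The sentences in 5.5 need only a consistency edit. The point should be corrected because the correction is nearly free and guards against clearing a dose on under-exposed patients.

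**What to change.** 1. **One assessability rule in the Protocol summary and 8.1.1, in terms of dose received.** A patient is assessable for escalation if he or she had a DLT, or received at least 75% of planned cycle-1 TG02 and at least 75% of planned RT (Group A) or TMZ (Group B). Drop the word compliance here.
2. **Replacement.** A patient without a DLT who falls below this is replaced for the escalation decision only.
3. **8.2.1.** State that patients replaced only under item 2 stay in the safety population. Without this, item 2 would remove them. Section 7.3.4 already includes all treated patients in overall safety analyses, and 8.2.2 reports excluded patients separately, so no data would be lost, but the main tables would omit them.
4. **Minor consistency edit.** In the four sentences of 5.5, add that the shortfall must be because of toxicity meeting the 5.2.1 dose-intensity criterion. Correct the pointer in 5.5.3.3.1 from 5.5.1 to 5.2.1.

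The cost is wording, plus possibly one or two replacement patients per group. At the assumed 2–5% shortfall rate, the expected number is 0.24–0.60 among 12 escalation patients.
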